8.2 Secondary outcome measures in the cohort study

- Levels of different cell signaling and cell cycle proteins (p16, p21, p53, NCX, mTOR,

Ras, Rb)

- Differences in parameters of cell death (apoptosis, stress resistance, mitochondrial damage) between groups
- Differences in telomere length, double strand breaks, chromosomal aberrations, heterochromatin between groups
- Differences in telomerase activity between groups
- Differences in endocrine parameters of fertility and nutritional regulation

8.3 Primary outcome measures in the randomized controlled trial

[figure not shown]
- Difference in the changes of insulin sensitivity (Matsuda index, ISI, HOMA-Index, QUICKI)
- Difference in the change of endothelial function

8.4 Secondary outcome measures in the randomized controlled trial

- Levels of different cell signalling and cell cycle proteins (p16, p21, p53, NCX, mTOR, Ras, Rb)
- Differences in parameters of cell death (apoptosis, stress resistance, mitochondrial damage) between groups
- Differences in telomere length, double strand breaks, chromosomal aberrations, heterochromatin between groups
- Differences in telomerase activity between groups

9. STUDY DESIGN

9.1 Schematic overview on study design

9.2 Duration of Study

It is anticipated that the study will run for 15 months (from first patient first visit until last patient last visit).

First patient first visit (FPFV):	May 2015
Last patient first visit (LPFV):	July 2016
Last patient last visit (LPLV):	August 2016
Data base lock:	September 2016
First results:	October 2016

9.3 Data collection

Once informed consent has been obtained, recruiting clinicians complete a CRF for each participant to record socio-demographic information, information about medical history and medications and dietary habits. Source documents comprise the CRF and hospital records, laboratory records and correspondence. All documents will be stored safely in a confidential manner. The subject will be referred to by a unique study subject number/code, their initials and date of birth on all study-specific documentations. The only exceptions will be the signed Consent Forms, Subject Identification log and subject clinical file, all of which will be stored securely by the clinical site. Source data will be made available for internal and external audits or inspections by regulatory authorities to authorised personnel only.

9.4 Randomization

Randomization for the pilot RCT will be designed and performed by the “Randomizer tool” provided by the Institute of Medical Informatics, Statistics and Documentation of Medical University Graz, Austria.

10. SELECTION AND WITHDRAWAL OF STUDY SUBJECTS

10.1 Subject Selection

The study population will consist of 100 healthy subjects. Fifty participants of them should already practice Alternate Day Fasting. Subjects in the ADF and control group will at least be matched by sex, weight and age. Subjects of the control group will be asked to participate in a pilot randomized controlled trial. A separate informed consent will be used for the intervention study.

10.2 Subject Recruitment

Healthy controls will be identified via Primary Care and adverts. Alternate Day Fasting subjects will be recruited by adverts and leaflets at Alternate Day Fasting Events.

10.3 Inclusion Criteria

- ✓ Age between 35 and 65 years,
- ✓ Body mass index in the range of 22.0 – 30.0 kg/m²,
- ✓ Fasting blood glucose <110mg/dL (without medication)
- ✓ LDL-cholesterol <180 mg/dL (without medication)
- ✓ Blood pressure <140/90 mmHg (without medication)
- ✓ Stable weight (change \pm 10%) for 3 months immediately prior to the study,
- ✓ No history of metabolic disorders or cardiovascular disease
- ✓ No acute or chronic inflammatory disorder
- ✓ No current medications to regulate blood sugar, blood pressure or lipids or hormones
- ✓ No heavy drinking (more than 15 drinks/week)
- ✓ No use of tobacco or recreational drugs within past 5 years
- ✓ No dietary restrictions (e.g. vegetarianism and vegan)

10.4 Exclusion Criteria

- ✓ Known Malignancy

- ✓ Women who are pregnant, breast-feeding or trying to become pregnant
- ✓ History of any chronic disease process that could interfere with interpretation of study results
- ✓ Women or men on hormonal supplementation or anti-conceptive hormonal medication for at least 2 months
- ✓ Therapy with antidepressants within past 6 months
- ✓ Regular therapy with acetylsalicylic acid

10.5 Withdrawal / Drop out of subjects

Each subject has the right to withdraw from the study at any time without prejudice or compromise to future care.

The investigator may discontinue or withdraw the subjects under the following circumstances:

- Significant protocol deviation
- Significant non-compliance with treatment regime or study procedures
- An adverse event that requires discontinuation of the study medication or results in inability to continue to comply with study procedures. If a subject is withdrawn due to an adverse event, the investigator will arrange for follow-up visits or telephone calls until the adverse event has resolved or stabilised.
- Consent withdrawn
- Lost to follow up
- Any other situation that may, in the opinion of the investigator, make it unsafe or inappropriate for the subject to continue in the trial

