4. SYNOPSIS

Study title	InterFast
Study design	Cohort study with an embedded randomized controlled pilot trial
Study participants	Healthy subjects and subjects who do already practice Alternate Day Fasting
Number of participants	90 (30 Participants in Alternate Day Fasting group and 60 participants in the control group). Those participants in the control group will be asked to participate in a short randomized controlled trial, where they will be either allocated to an Alternative Day Fasting group or another control visit.
Planned duration	18 months
Primary objective	The primary objective is to elucidate in which extent alternate day fasting influences human physiology in healthy individuals in both, the short and long term. Data of the pilot RCT will help to design a larger trial investigating Alternate Day Fasting in various groups of interest.
Secondary objectives	The secondary objective of this study is to define novel molecular markers of aging and age-related diseases.

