11.2 Visit Schedule for the cohort study

Visit 1

- Sufficient time will be provided and subjects will be encouraged to discuss all queries with the research team
- Informed consent for the study will be obtained by an investigator
- Biobank informed consent will be obtained by an investigator
- Check inclusion and exclusion criteria

- Demographics will be obtained: date of birth, gender, race, smoking status, alcohol consumption
- Weight
- Height
- Waist-Hip Ratio
- Medical history and standardized questionnaire on fertility outcomes
- Concomitant medication
- Vital signs: resting pulse and blood pressure
- Blood sampling
- ECG
- Food Frequency Questionnaire and Ferriman-Galway Score/Hamilton-Norwood Scheme
- Baseline blood tests (fasting): Full blood cell count, renal function tests, liver function tests,
- Pregnancy test in female woman of childbearing age
- Oral glucose tolerance test (OGTT)
- Application of the 24h blood pressure device
- Application of continuous glucose monitoring
- Application of accelerometer (Movisens®)

Visit 2 (9 ± 4 days after visit 1)

- Vital signs, Weight
- Physical examination
- Concomitant medication review
- Resting energy expenditure (REE)
- Measurement of endothelial function (EndoPAT 2000)
- Flow mediated dilatation (FMD)
- Blood sampling
- Oral glucose tolerance test (OGTT)
- IMT measurement
- Retinal vessel analyser
- Hand Grip Test
- Pulse wave analysis
- Echocardiography
- Collection and analysis of 24h blood pressure monitor
- Collection and analysis of accelerometer

- Removal of continuous glucose monitoring
- Dual-energy X-ray absorptiometry (DXA) and hand grip test
- Collection of sputum and faeces samples
- Buccal mucosa sampling
- Informed consent for RCT (healthy control group willing to participate in the RCT)
- Bioelectrical impedance analysis (BIA)
- Dry eye assessment (optional)

Visit 3 (2 weeks before visit 4) → only those subjects participating in the pilot RCT

- Application of continuous glucose monitoring

Visit 4 (4 weeks ± 1 week after visit 2) → only those subjects participating in the pilot RCT

- Vital signs, Weight
- Physical examination
- Concomitant medication review
- Resting energy expenditure (REE)
- Measurement of endothelial function (EndoPAT 2000)
- Flow mediated dilatation (FMD)
- Blood sampling
- Food Frequency Questionnaire
- Oral glucose tolerance test (OGTT)
- Removal of continuous glucose monitoring
- Collection of sputum and faeces samples
- Buccal mucosa sampling

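### Section 10.5 lets the investigator withdraw RCT participants who do not keep to the diet, so the Visit 4 primary outcomes can be lost selectively, mainly from the ADF arm

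*Protocol*

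**What the plan says.** Section 10.5 is the protocol's only withdrawal rule and covers cohort and RCT alike. It opens: "The investigator may discontinue or withdraw the subjects under the following circumstances". The grounds include significant protocol deviation and "Significant non-compliance with treatment regime or study procedures". Neither verb is defined, no threshold is given for what counts as significant, and no different consequence is attached to discontinuing and to withdrawing. The closing item covers any other situation that makes continuing in the trial unsafe or inappropriate, which implies that the grounds before it also end participation.

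Follow-up after withdrawal is promised in one case only: "If a subject is withdrawn due to an adverse event, the investigator will arrange for follow-up visits or telephone calls", until the event has resolved or stabilised. Another ground reads "An adverse event that requires discontinuation of the study medication", although the RCT assigns a diet.

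On the arms, the Synopsis says of the controls who join the RCT that "they will be either allocated to an Alternative Day Fasting group or another control visit". It also gives the pilot's purpose: "Data of the pilot RCT will help to design a larger trial investigating Alternate Day Fasting in various groups of interest".

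Section 8.3 makes the between-arm differences in change of insulin sensitivity and of endothelial function primary outcomes of the RCT. Sections 11.2 and 11.3 place OGTT, EndoPAT and FMD after randomisation at Visit 4 only, about four weeks after Visit 2. Visit 5, two years later, lists blood sampling and the food questionnaire but none of those three tests.

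**The concern.** A change score needs a post-randomisation value, and for these outcomes Visit 4 is the only scheduled source at four weeks. A participant withdrawn before Visit 4 contributes none. The mixed models named in section 12.26 would have no other four-week value from that person, and a two-year blood sample does not replace one.

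The ground is also unequal by design. Controls carry on as they were, so only the ADF arm has a new regimen to fail. If those withdrawn would have benefited less, the completers' difference moves from the effect of being assigned ADF towards the effect in people who keep to it. The as-randomised effect could then be estimated only under missing-data assumptions or as bounds. A larger trial needs to know both the effect of assignment and how many keep to the diet. Whether Visit 4 is sought from everyone is a rule of conduct, so it belongs in the protocol and cannot be repaired in an analysis plan.

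**Working it through.** **Pilot size.** Section 12.26 expects about 40% acceptance and about 10 per group. With its 50 controls, 0.40 × 50 / 2 = 10, so the figure reproduces. With the Synopsis figure of 60 controls, 0.40 × 60 / 2 = 12. One ADF participant lost is 1/10 = 10% or 1/12 = 8% of that arm's primary-outcome data.

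**Shift in the estimate.** The protocol gives no adherence or withdrawal rate, so these inputs are assumptions:
- q = non-adherent share of the ADF arm
- r = share of the benefit that non-adherers keep
- w = share of non-adherers withdrawn before Visit 4
- D = effect in adherers

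As-randomised effect = D[(1−q) + qr].

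Completers' effect = D[(1−q) + q(1−w)r] / [(1−q) + q(1−w)].

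Ratio of completers' to as-randomised effect:

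| r | w | q = 0.1 | q = 0.2 | q = 0.3 |
|---|---|---|---|---|
| 0 | 1 | 1.11 | 1.25 | 1.43 |
| 0.5 | 1 | 1.05 | 1.11 | 1.18 |
| 0 | 0.5 | 1.05 | 1.11 | 1.18 |
| 0.5 | 0.5 | 1.02 | 1.05 | 1.07 |

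Example, last row with q = 0.1: (0.925 / 0.95) / 0.95 = 1.02. If loss is unrelated to outcome the ratio is 1.00.

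**In HOMA-IR units.** Section 12.26 uses a mean of 3, an SD of 1.1 and a 15% effect for the cohort. Borrowing these for illustration, D = 0.15 × 3 = 0.45. The shift runs from 0.45 × (0.925/0.95 − 0.95) = 0.01 (q = 0.1, r = 0.5, w = 0.5) to 0.45 × (1 − 0.7) = 0.135, about 0.14 (q = 0.3, r = 0, w = 1).

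**Against the standard error.** With the cross-sectional SD and 10 per arm, SE = 1.1 × √(2/10) = 0.49; with 12 per arm, 0.45. No SD of change is given. Taking it as 1.1 × √(2(1−ρ)), with an assumed baseline-to-Visit-4 correlation ρ of 0.5 to 0.9, the SE is 0.49 to 0.22 (10 per arm) or 0.45 to 0.20 (12 per arm). The shift is below the SE in every case.

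**A second model.** Suppose the least compliant fraction f of the ADF arm is removed and compliance correlates c with the outcome. The ADF mean then shifts by c × φ(z_f)/(1−f) SD, where φ is the standard normal density and z_f the f-quantile.
- f = 0.1, c = 0.3: 0.3 × 0.195 = 0.06 SD
- f = 0.4, c = 0.5: 0.5 × 0.644 = 0.32 SD

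With an SD of 1.1 that is 0.06 to 0.35 HOMA-IR units. The SE with 10 v 10 is √(2/10) = 0.447 SD, again larger than the shift.

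**Precision.** Losing k ADF participants multiplies the SE by √(1/(n−k) + 1/n) / √(2/n). For k = 1, 2, 3 this is 1.03, 1.06, 1.10 with n = 10 and 1.02, 1.05, 1.08 with n = 12.

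**The case against.** The strongest reply is that the harm needs a trigger the schedule barely supplies. Between randomisation and Visit 4 the only scheduled contact is Visit 3, about 14 days after Visit 2, and it lists only the fitting of the glucose sensor. The food questionnaire, which looks back four weeks (section 12.8), is given at Visit 4 itself. Non-compliance must come to light outside the scheduled assessments, and the investigator must then choose to act, since the power is discretionary. If only a tenth of non-adherers are withdrawn (w = 0.1, also an assumption), the same formulas give ratios of about 1.00 (q = 0.1, r = 0.5) to 1.03 (q = 0.3, r = 0) and shifts of about 0.002 to 0.01 HOMA-IR units.

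It can be added that the grounds on study procedures and protocol deviation also reach controls, that the analyses are exploratory, that the 0.45 and 1.1 come from the cohort calculation, and that the section 9.1 schematic and the RCT consent form are not in the text at hand.

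All of this stands as a limit on size and likelihood. It does not change what 10.5 permits: nothing in the available text says that someone who stops ADF still attends Visit 4.

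**Conclusion.** The concern holds, with medium confidence, as a change that should be made. Section 10.5 gives a power that, if used before Visit 4, removes primary-outcome data mainly from one randomised arm without means of recovery. That the loss falls mainly on the ADF arm is an inference from the design, which the protocol does not state.

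The size is illustrative only. It runs from no bias, if loss is unrelated to outcome, to a 1.43-fold overstatement if 30% are non-adherent, gain nothing and are all withdrawn. With few withdrawals the ratio is close to 1. In a pilot of 10 to 12 per arm, sampling error exceeds the shift throughout. The gap weakens what the pilot can tell the larger trial but does not invalidate it.

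**What to change.** Add to section 10.5 that, for RCT participants:
- stopping or not keeping to the ADF regimen is recorded separately from study withdrawal and does not by itself end follow-up;
- the scheduled Visit 4 and Visit 5 assessments are sought from every randomised participant who has not withdrawn consent.

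The existing consent, adverse-event and safety grounds stay as they are, and the addition does not alter when anyone stops the diet. The reference to study medication must be reconciled with a dietary study. Analysis sets can be left to the SAP, but any adherers-only comparison should be labelled as no longer randomised.

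The cost is one or two sentences and one CRF line for the date and reason the diet was stopped. Both visits are already scheduled. The downside is a few more attended visits and a somewhat diluted effect estimate, because non-adherers are then counted.

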10.6 Payment to subjects

Reimbursement of reasonable travel expenses will be considered.

11. STUDY PROCEDURES

11.1 Schedule of study procedures of the cohort study

	Visit 1	Visit 2 (9 ± 4 days after visit 1)
Informed Consent	X	
Inclusion/exclusion criteria	X	
Demography, medical history	X	

Concomitant medication	X	X
Vital signs	X	X
Physical examination	X	
Blood sampling (FMD)	X	X
Dual-energy X-ray absorptiometry (DXA)		X
Oral glucose tolerance test (OGTT)	X	X (ADF group only)
Electrocardiography (ECG)	X	
Questionnaires (FFQ, Physical Activity)		X
Retinal vessels analyser		X
Continuous Glucose monitoring (CGM)	X	
Hand-Grip Test		X
Accelerometer (Movisens®)	X	
Endothelial function (EndoPat 2000)		X
Intima media thickness (IMT)		X
Pulse wave analysis		X
Buccal mucosa sampling	X	
24h blood pressure measurement	X	
Sputum sampling	X	
Faeces sampling	X	
Echocardiography	X	
Resting energy expenditure (REE)		X
Bioelectrical impedance analysis (BIA)		X
Dry eye assessment (optional)		X
Flow mediated dilatation (FMD)		X

11.2 Visit Schedule for the cohort study

Visit 1

- Sufficient time will be provided and subjects will be encouraged to discuss all queries with the research team
- Informed consent for the study will be obtained by an investigator
- Biobank informed consent will be obtained by an investigator
- Check inclusion and exclusion criteria

- Demographics will be obtained: date of birth, gender, race, smoking status, alcohol consumption
- Weight
- Height
- Waist-Hip Ratio
- Medical history and standardized questionnaire on fertility outcomes
- Concomitant medication
- Vital signs: resting pulse and blood pressure
- Blood sampling
- ECG
- Food Frequency Questionnaire and Ferriman-Galway Score/Hamilton-Norwood Scheme
- Baseline blood tests (fasting): Full blood cell count, renal function tests, liver function tests,
- Pregnancy test in female woman of childbearing age
- Oral glucose tolerance test (OGTT)
- Application of the 24h blood pressure device
- Application of continuous glucose monitoring
- Application of accelerometer (Movisens®)

Visit 2 (9 ± 4 days after visit 1)

- Vital signs, Weight
- Physical examination
- Concomitant medication review
- Resting energy expenditure (REE)
- Measurement of endothelial function (EndoPAT 2000)
- Flow mediated dilatation (FMD)
- Blood sampling
- Oral glucose tolerance test (OGTT)
- IMT measurement
- Retinal vessel analyser
- Hand Grip Test
- Pulse wave analysis
- Echocardiography
- Collection and analysis of 24h blood pressure monitor
- Collection and analysis of accelerometer

- Removal of continuous glucose monitoring
- Dual-energy X-ray absorptiometry (DXA) and hand grip test
- Collection of sputum and faeces samples
- Buccal mucosa sampling
- Informed consent for RCT (healthy control group willing to participate in the RCT)
- Bioelectrical impedance analysis (BIA)
- Dry eye assessment (optional)

Visit 3 (2 weeks before visit 4) → only those subjects participating in the pilot RCT

- Application of continuous glucose monitoring

Visit 4 (4 weeks ± 1 week after visit 2) → only those subjects participating in the pilot RCT

- Vital signs, Weight
- Physical examination
- Concomitant medication review
- Resting energy expenditure (REE)
- Measurement of endothelial function (EndoPAT 2000)
- Flow mediated dilatation (FMD)
- Blood sampling
- Food Frequency Questionnaire
- Oral glucose tolerance test (OGTT)
- Removal of continuous glucose monitoring
- Collection of sputum and faeces samples
- Buccal mucosa sampling
- Bioelectrical impedance analysis (BIA)

Visit 5 (2 years ± 4 weeks after Visit 4) → → only those subjects participating in the pilot RCT

- Vital signs, Weight
- Physical examination
- Concomitant medication review
- Blood sampling

- Food Frequency Questionnaire

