8. OUTCOMES

8.1 Primary outcome measures in the cohort study

- Differences in body composition (fat mass and lean body mass) between groups
- Differences in resting energy expenditure between groups
- Differences in insulin sensitivity (Matsuda Index, ISI, HOMA-Index, QUICKI) between groups
- Difference in glycaemic pattern (continuous glucose measurement) between the two groups
- Differences in endothelial function (Mean Intima media thickness, Reactive Hyperaemia Index, Stiffness Index, Aortic augmentation index) between groups
- Differences in mean 24h blood pressure between groups
- Differences in hormonal regulation (fertility, appetite hormones and others)

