12. METHODS

12.1 Oral glucose tolerance test (OGTT)

Various insulin sensitivity indices derived from a frequently sampled, extended oral glucose tolerance test (OGTT) will be calculated accounting for the various weighting of hepatic and peripheral insulin sensitivity expressed by the different indices. Insulin, C-peptide and glucose will be measured before and 15, 30, 60 and 120 minutes after ingestion of 75g glucose ([®]Glucoral 75 citron, Germania Pharmazeutika, Vienna). In addition, lipid-parameters (total cholesterol, triglycerides, HDL, LDL, free fatty acids) and a routine safety lab will be measured. The OGTT will be performed after an overnight fast (apart from water). A standard gauge cannula will be placed into a subcutaneous vein for blood sampling. In order to prevent blood clotting in the cannula and to keep the cannula working it will be occasionally flushed with sterile normal saline. A pre-meal blood sample will be taken (-5 mins) and then all subjects will be asked to drink the sugar solution over a period of 2-4 mins (time 0 min). During the OGTT further blood samples will be taken at 15, 30, 60, and 120 minutes. The blood at each time point will be placed into a fluoride oxalate tube (1ml) for plasma glucose and into a serum tube for analyses of insulin and c-peptide.

The insulin sensitivity index will be calculated from the OGTT according to four different equations: the

Matsuda-Index (IS_{OGTT}): $IS_{OGTT} = \frac{10000}{\sqrt{(glucose_0 * insulin_0) * (mean\ glucose * mean\ insulin)}}$,¹⁴ the HOMA-IR

(Homeostasis Model Assessment for Insulin Resistance): $HOMA - IR = \frac{FPG(\text{mmol/l}) * FSI(U/l)}{22.5}$ ¹⁵ and the

$QUICKI = \frac{1}{\log(insulin_0) + \log(glucose_0)}$ ¹⁶. The last equation was proposed by Stumvoll et al. (insulin

sensitivity index ISI): $ISI = 0.222 - 0.00333 * BMI - 0.0000779 * Ins_{120} - 0.000422 * age$ ¹⁷.

Beta-cell function will be estimated in the fasting state with $HOMA - \beta = \frac{20 * Insulin_0}{Glucose_0 - 3.5}$ ¹⁵ and during

the OGTT with the Stumvoll-Index: $1st\ phase = 1283 + 1.829 * Ins_{30} - 138.7 * Glc_{30} + 3.772 * Ins_0$ plus $2nd\ phase = 286 + 0.416 * Ins_{30} - 25.94 * Gluc_{30} + 0.926 * Ins_0$ ¹⁷ and the ratio

of the incremental insulin to glucose response over the first 30min during the OGTT $\frac{\Delta Insulin(30)}{\Delta Glucose(30)}$.

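### Table 11.1 and list 11.2 disagree on who has the Visit 2 OGTT; if the table applies and the list is the working order, the glucose load enters the CGM trace and the augmentation index in the ADF group only

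*Protocol*

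**What the plan says.** **Who has the test.** In table 11.1 the Visit 2 cell for the OGTT begins "X (ADF group only". The Visit 2 list in 11.2 has the entry "Oral glucose tolerance test (OGTT" with no mention of group. Section 12.1 says that "all subjects will be asked to drink the sugar solution over a period of 2-4 mins", but this describes how an OGTT is run and does not settle who has one at Visit 2.

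**Where it stands in the visit.** The Visit 1 list has the OGTT first and "Application of continuous glucose monitoring" after it. The Visit 2 list runs: resting energy expenditure, EndoPAT, flow mediated dilatation (FMD), blood sampling, OGTT, intima media thickness (IMT), retinal vessels, hand grip, "Pulse wave analysis", echocardiography, collection of the blood pressure and accelerometer devices, then "Removal of continuous glucose monitoring".

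**What depends on it.** The cohort primary outcomes in 8.1 include "Difference in glycaemic pattern (continuous glucose measurement) between the two groups" and "Differences in endothelial function (Mean Intima media thickness, Reactive Hyperaemia Index, Stiffness Index, Aortic augmentation index) between groups". Under 12.12 the augmentation index comes from pulse wave analysis. Neither 12.12 nor 12.18 places its measurement in relation to the glucose drink.

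**The concern.** A study procedure given to one exposure group and not the other can create a group difference that has nothing to do with the exposure. Here the procedure is a 75 g glucose drink. If the sensor is still worn, its excursion is recorded as part of that participant's glycaemic pattern. If pulse wave analysis follows, the augmentation index is read after glucose in one group and without it in the other. Trimming the CGM trace at analysis can remove the first problem. Nothing at analysis can restore pulse wave readings taken under different conditions in the two groups, so the order of measurements has to be fixed in the protocol.

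**Working it through.** **1. Is the sensor still on at Visit 2?** Visit 2 is 9 ± 4 days after Visit 1, that is day 5 to day 13. Section 12.18 plans 14 days of wear, and 11.2 makes Visit 2 the removal visit. So the sensor is planned to be on at arrival. Section 12.18 also describes wear of up to 7-14 days, so a shorter-lived sensor could have stopped before a late Visit 2.

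**2. What follows under each reading?**

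| Who has the Visit 2 OGTT | List order followed | Consequence |
|---|---|---|
| ADF only (table 11.1) | yes | Load in trace and before pulse wave analysis, ADF group only |
| Everyone (list 11.2) | yes | Same load in both groups; no group-specific artefact, but a test drink in every trace |
| Either | no | Not determined by the protocol |

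The Visit 1 load falls before sensor application on list order, so it lies outside the trace in both groups.

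**3. Which endothelial measures are exposed?** On list order, EndoPAT (reactive hyperaemia index, RHI) and FMD come before the drink and are not exposed; pulse wave analysis (augmentation index) comes after. IMT is also listed after the drink, but it is a wall-thickness measure and nothing is claimed for it here. The protocol does not say which method yields the Stiffness Index, so its position cannot be determined.

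**4. Size of the CGM effect.** The protocol gives no figure to reproduce. Assumptions, none from the documents: mean excursion *e* = 2 to 3 mmol/L over 2 h; usual within-person SD 0.9 mmol/L; 0.5 to 1 h of the test above 7.8 mmol/L; 1-2% of time normally above that level. *H* is hours of wear.

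- Mean shift = *e* × 2/*H*. At 9 days, *H* = 216: 2 × 2/216 = 0.019 and 3 × 2/216 = 0.028 mmol/L.
- SD = √(0.9² + (2/*H*)*e*² − shift²). At 9 days: √(0.81 + 0.0370 − 0.0003) = 0.920, up 2.2%; √(0.81 + 0.0833 − 0.0008) = 0.945, up 5.0%.
- Time above range, absolute: 0.5/216 = 0.23 and 1/216 = 0.46 percentage points. Relative to the assumed 1-2% (2.16 to 4.32 h): 0.5/4.32 = 12% to 1/2.16 = 46%.

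| Wear | Share of trace (2 h/*H*) | Mean shift, mmol/L | Time above range, percentage points |
|---|---|---|---|
| 5 days (120 h) | 1.67% | 0.033-0.050 | 0.42-0.83 |
| 9 days (216 h) | 0.93% | 0.019-0.028 | 0.23-0.46 |
| 13 days (312 h) | 0.64% | 0.013-0.019 | 0.16-0.32 |

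A second set of assumptions (excursion 20 to 60 mg/dL, SD 15 to 20 mg/dL) gives the same picture at 9 days: mean up 0.19 to 0.56 mg/dL, SD up 0.5% to 7%.

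The peak of a trace would be the OGTT value whenever that exceeds everything else recorded in the wear period. How often this happens cannot be derived from the documents.

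**5. The randomised pilot.** Its participants come from the control group. Both arms have the Visit 4 OGTT, which is listed just before sensor removal. Under table 11.1 their Visit 1-2 trace has no load while the Visit 3-4 trace ends with one. Change within an arm is affected; the comparison between arms is balanced.

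**The case against.** The group restriction comes only from the table, which states no order. The order comes only from the list, which states no restriction. A reader might infer that the protocol as written builds a differential bias into two primary outcomes, but that requires combining two passages that contradict each other. If the list governs both points, nothing is group-specific. This stands, and it is why the point is conditional.

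Nor is the list declared to be a clock order. It names the hand grip test twice at Visit 2, and it disagrees with the table on the visit for other items, such as echocardiography. This also stands, and the augmentation-index part rests on list order alone. Still, no other order is given, and a site would have reason to follow this one.

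The CGM window could be set in the statistical analysis plan that 12.26 announces, which is not at hand. Silence on trimming is therefore not itself a fault. That answer does not reach the pulse wave readings.

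Finally, 8.1 names only glycaemic pattern. Peak, SD and time above range are plausible summaries, not stated endpoints, and the 12-46% relative rise is large mainly because the assumed baseline is small.

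**Conclusion.** The conflict between 11.1 and 11.2 on who has the Visit 2 OGTT is certain and must be reconciled. The group-specific artefact is conditional on the table applying and the list being the working order. On those conditions it reaches the CGM trace and the augmentation index, which is one of four measures named under endothelial function; RHI and FMD are not affected.

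The CGM effect, on assumed inputs, is negligible for the mean, a few percent for the SD, and about 0.2-0.5 percentage points of time above range at 9 days, with the peak potentially most exposed. A reader might also infer that the augmentation index is pushed in a known direction because only one group drinks. The documents do not support that: under the table it is known which group drinks, but neither the size nor the sign of any shift. The randomised pilot is touched only through within-arm CGM change, and CGM is not among the primary outcomes legible in 8.3.

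The point is worth correcting because the change costs almost nothing and a difference in measurement conditions cannot be repaired afterwards.

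**What to change.** 1. Reconcile table 11.1 and the Visit 2 list in 11.2 on which participants have the Visit 2 OGTT.
2. State in 11.2 that pulse wave analysis and the other Visit 2 vascular measurements are completed before the glucose drink in every participant who has one. On list order EndoPAT and FMD already are, so only the items now listed after the OGTT move. Visit 4 needs no reordering of vascular measures.
3. State in 12.18, or in the statistical analysis plan, that the CGM analysis window ends on arrival at Visit 2 and at Visit 4, so that no study glucose load is in any trace.

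The cost is a few hours of CGM data per participant and a slightly later OGTT start on the visit day. No procedure is added.
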